5.3 Exploratory Outcomes

5.3.1 Perceived Income Adequacy

Perceived income adequacy was assessed using the validated single-item Perceived Income Adequacy tool, which measures current difficulty making ends meet.⁹⁸⁻¹⁰⁰ Response options are given on a Likert Scale ranging from very difficult to very easy. Endorsements of *neither easy nor difficult*, *easy*, or *very easy* indicate income is

perceived as adequate, and *very difficult*, and *difficult* indicate income is perceived as inadequate. Perceived income adequacy will be analyzed as a binary outcome.

5.3.2 Subjective Social Status

Subjective social status refers to an individuals' perceived position within the social hierarchy relative to others in their community and/or nation¹⁰¹, and has been shown to adversely impact health outcomes beyond objective measures of socioeconomic status (e.g., income).¹⁰² This outcome was assessed using the validated MacArthur Scale of Subjective Social Status national and community ladders.¹⁰³ Using a picture of a ladder, respondents used a visual analog scale to place themselves on a ladder rung according to their current perceived social standing relative to others in their nation and in their community. Both ladder scales use a discrete scale ranging from 1 (bottom rung indicates lowest status) to 10 (top rung indicates highest status), with a higher score indicating higher perceived social status in relation to others within ones' nation and community. Subjective social status will be analyzed as a continuous outcome.

5.3.3 Work Productivity and Activity Impairment

Work productivity and impairment was assessed using the validated 6-item Work Productivity and Impairment tool. The questions measure impairments in paid work and regular activities due to health issues in the past 7 days.^{104, 105} The tool yields 4 percentage scores including absenteeism (work time missed), presenteeism (impairment at work/reduced on-the-job effectiveness), work productivity loss (overall work impairment), and activity Impairment (impairment in non-work activities). Higher scores indicate greater productivity loss and/or activity impairment. Work productivity and activity impairment will be analyzed as a continuous outcome.

5.3.4 Medication Adherence

Adherence to prescribed medications was assessed using the validated single-item Medication Adherence measure, which is a visual scale measuring how often participants took their prescribed medication in the past 7 days.¹⁰⁶ Response values range from 0-100% with anchors at 0% (none at all) – 50% (half of prescribed doses) – 100% (all doses of prescribed medications). Higher percentage values indicate greater medication adherence. Medication adherence will be analyzed as a continuous outcome.

5.3.5 Physical Activity Level

Physical activity level was assessed using a validated single-item physical activity tool, which measures how many days during the past 7 days participants took part in 30 minutes or more of moderate to vigorous exercise.¹⁰⁷ Response values range from 0 (0 days) to 7 (7 days) with higher numbers indicating higher physical activity levels. Physical activity level will be analyzed as a discrete outcome.

5.4 Non-RCT Outcomes

The following outcomes are included in the planned manuscripts, although data were not collected as part of the RCT. Results for other FoodRx studies will be reported in manuscripts described elsewhere.

5.4.1 Incentive Usage

Incentive usage will be assessed as a count of the number of weeks participants earned the incentive and/or redeemed the incentive. The total possible weeks for both earning and redeeming the incentive is 52 weeks.

5.4.2 Healthcare Costs

Annual total healthcare costs for each participant will be calculated using provincial administrative databases, with costs representing the sum of hospital costs, emergency department and day surgery costs, physician service costs, and publicly funded pharmacy costs. Hospital costs will be estimated using the Discharge Abstract Database (DAD) through resource intensity weights multiplied by cost per weighted case. Emergency department and day surgery costs will be derived from the National Ambulatory Care Reporting System (NACRS). Physician service costs will be calculated from Practitioner Claims data, and community pharmacy costs

will be obtained from the Pharmaceutical Information Network. All analyses will be conducted from the public healthcare payer perspective and reported in 2025 Canadian dollars, with costs analyzed as a continuous variable that accounts for the potential presence of large numbers of zero values and the non-negative nature of cost data.

6. Statistical Principles

6.1 Regression Model Assumptions

We will assess whether the assumptions for each regression model are met, and will take appropriate corrective steps if violations are identified. In analyses where the proportional-odds assumption is violated, we will use generalized proportional odds models to preserve the ordinal nature of the outcome(s) in question and allow covariate effects to vary across thresholds as necessary. In analyses with severe violations, we will use multinomial logistic regression models.

6.2 Hypothesis Testing

For hypothesis testing, confidence intervals are set at 95% and statistical significance is set at $p < 0.05$. Confidence intervals and absolute p-values will be reported in all manuscripts, regardless of statistical significance. Adjusted and unadjusted estimates will be reported.¹⁰⁸ When interpreting results, emphasis will be placed on effect sizes, confidence intervals, and clinical relevance rather than statistical significance alone.

6.3 Analysis Population

Analyses will be intention-to-treat using all available data for parameter estimation of primary, secondary, and exploratory outcomes.

6.4 Missing Data

Missing data due to withdrawal or loss-to-follow-up is expected despite mitigation strategies that were in place to reduce missingness. We will examine missing data during cleaning to 1) document potential reasons for missingness, 2) examine the plausibility of a missing at random assumption, and 3) identify auxiliary covariates that may be predictive of outcomes to inform our assumptions and handling of missing data.¹⁰⁹

Missing data will be handled using full information maximum likelihood under a missing at random assumption, provided this assumption appears plausible after examining the data.^{109, 110} Preliminary auxiliary variables, which will be assessed for each outcome, are detailed in Section 7.

To investigate the impact of different assumptions regarding missing data on estimated program impacts, we will use Markov chain Monte Carlo multiple imputation regardless of the percentage of missingness, inverse probability weighting, and available case analysis.¹¹¹⁻¹¹³ We will also use pattern mixture methods models¹¹⁴ to explore the robustness of study findings to the assumption that data are not missing at random.^{109, 115}

6.5 Multiple Comparisons

We have used current guidelines for multiplicity to assess the risk of increased Type I error rates in this study.^{116, 117} As such, we will not adjust for multiple comparisons given the RCT 1) is exploratory, 2) includes 2 distinct treatment arms, 3) has a single pre-specified primary outcome that is the basis for statistical inference, 4) positions secondary and exploratory outcomes as supportive to the primary outcome and as hypothesis-generating, 5) did not include interim analyses, 6) will account for repeated measures using mixed-effect models with group by time and time-treatment interactions (testing for contrasts at each timepoint)¹¹⁷, 7) includes pre-specified exploratory sub-group analyses, and 8) includes exploratory sensitivity analyses to assess treatment consistency across groups. In addition, multiplicity adjustments increase the chance of type 2 errors, and assume all null hypotheses are true (i.e., all positive results are false positives). Lastly, these adjustments assume all outcomes are independent, which is not the case for the FoodRx RCT as many outcomes are related (e.g., blood lipids, systolic and diastolic blood pressure). All results will be interpreted with caution considering p-values,

confidence intervals, and effect sizes. Findings for secondary results, and secondary and exploratory outcomes will be presented as exploratory.¹¹⁸

6.6 Statistical Software

Statistical analyses will be conducted in Stata¹¹⁹, and R¹²⁰ using versions specified in the final manuscripts.

7. Analyses

To describe the analyses, we have grouped all outcomes according to the manuscript in which they will be reported. Mixed-effects linear, logistic, and/or non-linear regression models will be used to assess group differences in outcomes at baseline and post-intervention.

The incentive program was paused after 11 weeks due to problems with delivery of the incentive. The incentive program resumed 12 weeks later when the issues were rectified. This restart impacted 31 participants who had completed baseline data collection, been randomized, and begun the program. Those who chose to remain in the program completed baseline data collection a second time, resulting in duplicate baseline measures. The following analyses will include the second set of baseline data unless otherwise specified (i.e., sensitivity analysis).

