3.4 Randomization and Blinding

Prior to randomization, participants completed baseline data collection and received the healthy food prescription. Researchers randomized participants to either the FoodRx (n=299) or comparison (n=297) group with a 1:1 allocation ratio using a computer-generated, concealed, blocked randomization sequence in REDCap (Research Electronic Data Capture)⁴¹ created by an independent statistician. Blocking variables included gender identity (woman, man), recruitment location (urban setting, rural setting, Indigenous primary care clinic), and baseline A1C (6.5-8.5%, 8.6-12%). The intervention group received both a healthy food prescription and a healthy food incentive. The comparison group received a healthy food prescription alone.

Due to the nature of the intervention, participants were not blinded to their allocation; however, they were blinded to study objectives. Participants in the comparison group were also blinded to the details of the healthy food incentive, including its monetary value and eligible foods. Care providers and researchers who collected and analyzed the data were blinded to treatment allocation with the exception of a research assistant who assisted participants in the intervention group throughout the trial.

4. Trial Population

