4.2 Sample Size

The sample size calculation was based on A1C, the primary outcome for the RCT. A mean baseline A1C of 8.5% (SD=1.4%) was expected in our population based on local administrative data.⁴⁴ For 90% power to detect a minimally important clinical difference in A1C of 0.5%⁴⁵, 594 participants were required assuming 5% type 1 error, 30% attrition⁴⁶, and potential design effects based on sampling in different primary care clinics and communities (25% inflation).

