7.4 Primary Manuscript

This paper will report results for 12-month A1C, our primary outcome, along with secondary and exploratory outcomes at 6-, 12-, and/or 18-months, including blood glucose levels, clinical health markers, and need for antihyperglycemic medication.

12-month A1C, Primary Outcome

We will assess the intention to treat effect of group assignment on mean A1C at 12-months as a continuous outcome using mixed-effects linear regression. The primary test will be the group \times time interaction contrast at 12-months (i.e., post-intervention), which estimates between-group differences in mean A1C from baseline to 12 months. Models will be adjusted for baseline A1C to estimate treatment effect while holding baseline A1C constant, and additional blocking variables (gender, recruitment location). To improve the precision of effect estimates, models will also be adjusted for age, race/ethnicity, educational attainment, number of children living in the home, and diabetes duration. Additionally, all models will include a data source indicator variable (study measured vs administrative health data), group (FoodRx vs comparison), collection timing (number of days measurement was taken since baseline), and restart cohort indicator variable (did not restart vs did restart). We will include random intercepts for participants (participant study ID) to account for within-subject correlation due to repeated measures, and for primary care clinics (clinic study ID) to account for clustering of participants within clinics. Missing data for covariates will be addressed using full information maximum likelihood.

We will conduct subgroup analyses for 12-month A1C by baseline household food insecurity severity (marginal, moderate, severe), gender (man, woman, gender diverse), recruitment location (urban setting, rural setting, Indigenous primary care clinic), Indigenous identity, baseline A1C ($\leq 8.5\%$, $\geq 8.6\%$), and baseline insulin use (no, yes).

We will conduct dose-response analyses to examine whether 12-month A1C differs based on the total value of incentives redeemed, a continuous variable, in the first 6 months for the mid-intervention analysis, and in the full 12-months for the post-intervention analysis.

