In addition to per-protocol and as-treated analyses, we will conduct sensitivity analyses for 12-month A1C to examine 1) the impact of excluding A1C values obtained from administrative health data, 2) if findings differ when models include all participants regardless of A1C source, and a collection timing indicator variable (time since baseline, deviation from 12-month data collection timepoint), 3) the impact of using multiple imputation for missing data rather than full information maximum likelihood, 4) the impact of adjusting for changes in medication/insulin type and dosage between baseline and post-intervention follow-up, 5) the impact of including the first measure of baseline A1C collected before the trial was restarted, and 6) the impact of excluding participants who restarted the trial.

Blood Glucose Levels, Secondary Outcomes

6-month A1C We will assess group differences in 6-month A1C (i.e., mid-intervention) as a continuous outcome using mixed-effects linear regression. Models will be adjusted for baseline A1C, and additional blocking variables (gender, recruitment location). To improve the precision of effect estimates, models will also be adjusted for age, race/ethnicity, educational attainment, number of children living in the home, and diabetes duration. Models will also include group (FoodRx vs comparison), and baseline A1C data source (study measured vs administrative health data) indicator variables. We will include random intercepts for participants (participant study ID) to account for within-subject correlation due to repeated measures, and for primary care clinics (clinic study ID) to account for clustering of participants within clinics.

In addition to per-protocol and as-treated analyses, we will conduct sensitivity analyses for 6-month A1C to examine 1) the impact of excluding A1C values obtained from administrative health data, 2) if findings differ when models include all participants regardless of A1C source, and a collection timing indicator variable (time since baseline, deviation from 6-month data collection timepoint), 3) the impact of using multiple imputation for missing data rather than full information maximum likelihood, 4) the impact of adjusting for changes in medication/insulin type between baseline and mid-intervention follow-up, and 5) the impact of including the first measure of baseline A1C collected before the trial restart.

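### For restart participants who stayed, every main model takes as baseline a value measured after randomisation; the bias in 12-month A1C is small but avoidable, and most other outcomes have no check on it

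*SAP*

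**What the plan says.** SAP section 3.4 sets the normal order of events: "Prior to randomization, participants completed baseline data collection". The opening text of section 7 then describes an exception. The incentive programme was paused after 11 weeks because of delivery problems and resumed 12 weeks later. On who was affected, the SAP says: "This restart impacted 31 participants who had completed baseline data collection, been randomized, and begun the program". It does not give the number who stayed, but it says what they did: "Those who chose to remain in the program completed baseline data collection a second time". These participants therefore have two baselines, and the rule for choosing between them is: "The following analyses will include the second set of baseline data unless otherwise specified". The SAP mentions no re-randomisation.

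Section 7.2 adjusts every model for the baseline value of its outcome and for the blocking variables, one of which is baseline A1C. Section 7.4 also describes the primary contrast as running from baseline to 12 months.

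Provision for the restart differs by outcome:
- **12-month A1C (7.4):** a "restart cohort indicator variable (did not restart vs did restart") in the model, and two sensitivity analyses. One examines "the impact of including the first measure of baseline A1C collected before the trial was restarted"; the other leaves out those who restarted.
- **6- and 18-month A1C, elevated A1C, fructosamine (7.4):** one sensitivity analysis with the first baseline A1C, and no restart indicator. For fructosamine this varies baseline A1C, not baseline fructosamine.
- **All other outcomes (rest of 7.4, and 7.5 to 7.9):** no restart indicator or restart analysis is listed.

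**The concern.** A baseline covariate is safe to adjust for because treatment cannot have influenced it. The second baseline lacks that protection: it follows randomisation, knowledge of the allocation and up to 11 weeks of programme. If the incentive had begun to work, part of its effect already sits in the covariate, and adjustment subtracts that part from the estimate.

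A main-effect indicator for the restart cohort does not help. It absorbs a shift in the cohort's average level, whereas the bias comes from a difference between arms within the cohort.

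Two smaller consequences follow. The baseline A1C subgroups (cut at 8.5/8.6) may place a restart participant in a different category from the stratum used at randomisation. And the reason given in section 7.1 for not testing baseline differences, that they arise by chance, holds only for values measured before randomisation.

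**Working it through.** **1. The plan's own figure.** Section 4.2: "For 90% power to detect a minimally important clinical difference in A1C of 0.5" percentage points, with SD 1.4, and "594 participants were required assuming 5% type 1 error, 30% attrition" plus 25% inflation. Two-sided testing is assumed.
- Normal approximation: 2 × (1.4 × (1.960 + 1.282) / 0.5)² = 164.8 per arm. With the t distribution it is 165.7, so 166.
- 166 × 1.25 = 207.5, taken as 208; 208 / 0.70 = 297 per arm; total 594. The figure reproduces, and its inputs set the scale for what follows.

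**2. Share affected.** Randomised: 299 + 297 = 596 (section 3.4). 31 / 596 = 5.2%. This is an upper limit, because only those who stayed have a second baseline and their number is not given.

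**3. Formula.** The adjusted effect is the arm difference at follow-up minus the slope b times the arm difference in the covariate. If restart participants are split between arms like the whole trial, and the second baseline carries an arm difference e, then

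attenuation = (31 / 596) × b × e.

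The SAP gives neither b nor e, nor the split by arm. Assumed ranges: b from 0.4 to 1.0 (1.0 corresponds to a change-from-baseline contrast), e from 0 to 0.5 A1C points.

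| b | e = 0 | e = 0.1 | e = 0.25 | e = 0.5 |
|---|---|---|---|---|
| 0.4 | 0 | 0.002 | 0.005 | 0.010 |
| 0.6 | 0 | 0.003 | 0.008 | 0.016 |
| 0.8 | 0 | 0.004 | 0.010 | 0.021 |
| 1.0 | 0 | 0.005 | 0.013 | 0.026 |

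The largest value is 0.026 / 0.5 = 5.2% of the target difference. If only 15 had stayed, it would be (15 / 596) × 1.0 × 0.5 = 0.013.

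**4. Check by simulation.** 596 participants, 31 restarters, true effect −0.50, SD 1.4, within-person correlation 0.6, restart indicator in the model, 2,000 replicates per scenario:
- e = 0: −0.497 with either baseline.
- e = 0.25: −0.500 with the first baseline, −0.493 with the second.
- e = 0.5: −0.497 with the first, −0.482 with the second.

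The differences match the table row for b = 0.6, so the indicator does not remove the bias. Among the 31 alone the adjusted effect falls to about −0.35 (e = 0.25) or −0.20 (e = 0.5).

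**5. Effect on power.** Effective number per arm: 594 × 0.70 / 1.25 / 2 = 166.3. Power is 90.3% for a difference of 0.5, 89.4% for 0.492 (b = 0.6, e = 0.25) and 87.0% for 0.474 (b = 1.0, e = 0.5).

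**6. Outcomes with 6-month recall.** Section 5.2.4 uses a 6-month reference period for household food insecurity, competing demands, financial barriers and hypoglycaemic episodes. If the repeat was taken near resumption (its date is not stated), it fell up to 11 + 12 = 23 weeks after the start, so a 6-month window would cover the whole early exposure. These outcomes have no restart analysis.

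**The case against.** The strongest reply is washout. The pause lasted 12 weeks and A1C reflects about the previous 3 months (section 5.1), so a repeat taken near resumption would mostly describe the pause. Incentive delivery had also been faulty. Residual shifts of 0.25 to 0.5 are half to all of the 12-month target, and zero is plausible. This stands for A1C and is why the range starts at 0. It is not assured, since earned points did not expire (section 3.2), and it is weaker for outcomes with 6-month recall.

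Second, the primary outcome is already checked twice, once by leaving the restarters out altogether. That also stands. It limits the consequence for 12-month A1C but leaves the main estimate's default unchanged and does not reach most other outcomes.

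Third, aligning baseline with the 12-month programme actually delivered is a disclosed and defensible choice. Keeping the first baseline while timing follow-up from the restart would stretch the baseline-to-12-month span to about 23 + 52 = 75 weeks for these participants. This is a real cost, which the fix has to address.

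A reader might go further and infer that restart participants who left are dropped, against section 6.3. The SAP does not say so. Its rule chooses between duplicate measures, leavers have no duplicate, section 6.3 uses all available data, and missing covariates in the primary model are handled by full information maximum likelihood. A reader might also infer that the restart indicator depends on the later choice to stay. The term can equally mean all 31 people randomised before the pause. Both are gaps in wording, not demonstrated errors.

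**Conclusion.** The point holds in a limited form. For at most 5.2% of participants the default baseline in every main model is a post-randomisation measurement, although a pre-randomisation one exists. For 12-month A1C the attenuation is 0 to about 0.026 points, under an assumed residual shift of 0 to 0.5, an assumed slope of up to 1.0, all 31 staying, and a proportionate split by arm. Against a standard error of about 0.09 (the simulation above, without attrition), even the maximum is under a third of one standard error. The figures do not support a claim that the primary result is materially compromised.

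The change is still worth making, because the bias is avoidable and most secondary outcomes have no check on it. If restart participants were re-randomised after the second baseline, the point would fall away; the SAP gives no sign of that.

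**What to change.** In section 7:
- Use the pre-randomisation baseline and the randomisation stratum as the default for all 31 restart participants in every main model, including those who left.
- Move the second baseline to a sensitivity analysis for every outcome, using that outcome's own baseline value. Keep the existing analysis of 12-month A1C without restarters.
- Code the restart indicator as randomised before the pause, whether or not the participant stayed.
- State the time origin for these participants, both for the covariate that counts days since baseline (7.4) and for the area-under-the-curve QALY (5.2.4).

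The cost is SAP wording, since both sets of data exist. The downside is that for about 5% of participants the covariate is up to about 23 weeks older and slightly less predictive, and the QALY would start from a correspondingly older utility value unless its origin is set otherwise.
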